8.2.3. Diet and Study restriction(s)

On the Day 1, the subjects will be allowed to eat at the following times relative to drug administration:

T4h standardized lunch;T12h standardized dinner.

Meals should always be taken after the PK sampling, in case both coincide.

On the other hospitalization days, a standard breakfast will be served. Water supply will be between 1,5 and 2L for each 24-hour period.

During the hospitalization, the subject will be restricted to indoor activities (no exercise), rest and will not leave the Clinical Pharmacology Unit.

Apart from the hospitalization times, the subject will be requested to follow a stable lifestyle throughout the duration of the trial with no sport activity.

Throughout the duration of the study, the consumption of nicotine will be completely prohibited.

The consumption of alcohol and xanthine bases-containing beverages will be allowed between screening and 24 hours before Day-1 but will be stopped at least 24 h before Day-1 and throughout the study duration.

The consumption of grapefruit and grapefruit-containing products will be stopped at least 7 days before Day-1 and throughout the study duration.

8.2.4. Sampled blood volume

8.3. Adverse Event and Reporting

8.3.1. Definitions

By the following is understood:

Adverse Event (AE), any untoward medical occurrence in a patient or clinical trial subject administered an investigational medicinal product and which does not necessarily have a causal relationship with this treatment.

It can therefore be any unfavourable and unintended sign (e.g. an abnormal laboratory finding), symptom, or disease temporally associated with the use of a medicinal product, whether or not considered related to the medicinal product.

Definition of an AE includes worsening (in severity and frequency) of pre-existing conditions ("Medical history") before first Investigational Medicinal Product (IMP) administration and abnormalities of procedures (i.e. ECG, X-ray...) or laboratory results which are assessed as "clinically significant".

Clinically Significant Laboratory/Procedures Abnormalities:

For every laboratory assessment, the investigator will evaluate if the laboratory test is normal or abnormal. If abnormal (after repeat test as required), the investigator will assess if this finding is clinically significant or not. If a laboratory parameter is abnormal and clinically significant, it should be reported as an AE.

An abnormal laboratory/procedure result must be compared with the previous value taking into account normal values in the studied population/country.

An AE is a new fact after the administration of the first dose of the study drug or a worsening in the condition; in the case of abnormal laboratory/procedure tests results, it is an increase in severity (clinical intensity) of the abnormality which is judged clinically significant by the investigator.

Laboratory/procedures (i.e. ECG...) abnormalities should be assessed as "clinically significant" (and therefore have to be reported as an AE) if they meet at least one of the following conditions:

- The abnormality suggests a disease and/or organ toxicity AND this abnormality was not present at the screening visit or is assessed as having evolved since the screening visit
- The abnormality requires medical intervention or concomitant therapy

Furthermore, laboratory abnormalities associated with clinical signs and symptoms will also be considered clinically significant.

When reporting an abnormal laboratory result as an AE, a clinical diagnosis should be recorded rather than the abnormal value itself, if available. However, in these cases, the AE should be recorded as the syndromic clinical diagnosis (e.g., acute pancreatitis instead of each finding separately: high levels of amylase, high levels of lipase, abdominal pain and vomiting; e.g. "hypokalemia" rather than "decreased potassium levels").

Temp-UPC-853-C du 07/08/2017

Adverse Drug Reaction (ADR),

All untoward and unintended responses to an IMP related to any dose administered i.e. any AEs judged by either the reporting Investigator or the Sponsor as having a reasonable possibility of a causal relationship with the IMP. This means that there are facts (evidence) or arguments to suggest a causal relationship between the event and the IMP (see definition of causality in 8.3.5.).

Serious Adverse Event or Reaction, a Serious Adverse Event (SAE) or Reaction (SAR) is any untoward medical occurrence or effect that at any dose:

- Results in death;
- Is life-threatening (at the time of the event): in this context refers to an AE in which the patient was at risk of death at the time of the AE; it does not refer to an AE that hypothetically might have caused death if more severe;
- Requires in patient hospitalization or prolongation of existing hospitalization: i.e. the AE requires at least an overnight admission or prolongs a hospitalisation beyond the expected length of stay;
- Results in persistent or significant disability or incapacity: i.e. the AE resulted in a substantial disruption of the subject's ability to conduct normal activities;
- Is a congenital anomaly or birth defect i.e. an AE outcome in a child or foetus of a subject exposed to the IMP before conception or during pregnancy;
- Is an important medical event: i.e., AE is medically significant: medical and scientific judgment should be exercised in deciding whether other situations should be considered serious events/reactions, such as important medical event that may not be immediately life-threatening or results in death or hospitalization but may jeopardize the subject or may require intervention to prevent one of the other outcomes listed in the above definition should also usually be considered as serious.
 - In addition, any suspected transmission via a medicinal product of an infectious agent is also considered a serious adverse event/reaction.

Unexpected adverse reaction, an unexpected adverse reaction is an adverse reaction, whose nature, severity or outcome is not consistent with the applicable product safety reference information on the IMP i.e. the Investigator's Brochure for an unauthorized IMP or the Summary of Product Characteristics (SmPC) for an authorized product which is being used according to the terms and conditions of the marketing authorization.

Suspected Unexpected Serious Adverse Reaction (SUSAR), a suspected AE related to an investigational medicinal product that is both unexpected and serious.

8.3.2. Reference documents for expectedness assessment

The reference document for expectedness assessment of SAE related to study product for the present study is the Investigator Brochure (IB) currently in force at the time of SAE occurrence.

The reference document for ORA-Sweet® is attached in appendix III.

8.3.3. Recording of events

Any AE (including laboratory test/procedures "clinically significant" abnormalities, intercurrent illnesses or injuries, and/or study procedures related AE) reported spontaneously by the subjects, or observed by the Investigator, after IMP administration, will be recorded according to the procedures in force at EUROFINS OPTIMED.

Any untoward medical event, which occurs from the time of signed Informed Consent to the time of IMP administration, will be classified as "pre-dose event" (not considered an adverse event *per se*) and will be recorded according to the procedures in force at EUROFINS OPTIMED.

Any untoward medical event which occurs after the completion of the clinical trial and that is possibly reported by the Investigator to EUROFINS OPTIMED will be classified as a "post-study event" and will be recorded according to the procedures in force at EUROFINS OPTIMED.

8.3.4. Analysis of events

8.3.4.1. By the investigator

Each AE is to be classified by the investigator (in this order):

- For severity
- For causality
- As serious or non- serious

8.3.4.1.1. Grading of Adverse Event severity

The Investigator will evaluate each event with regard to its severity. The severity of the AEs will be determined in the following manner:

Mild: The subject is aware of the event or symptom, but the event or symptom is easily tolerated

(e.g. no reduction in daily activities is required).

Moderate: The subject experiences sufficient discomfort to interfere with or reduces his or her usual

level of activity.

Severe: Significant impairment of functioning: the subject is unable to carry out usual activities

and/or the subject's life is at risk from the event.

Life-Threatening: The subject is at significant risk of life; it does not refer to an event which hypothetically

might have caused death if it were more severe (life-threatening consequences, urgent

intervention required).

Death: Death related to an event.

When the intensity of an AE changes over time, each change in intensity will be recorded in the source documents until the event resolves. However, only one AE and the maximum intensity will be recorded in the eCRF for each separate event. If the AE resolves but then recurs, each will be recorded as a separate AE, with the appropriate start and stop times.

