1.3. Summary of the known and potential risk and benefits to human subjects

There is no known (identified) risks to human subjects.

The subjects enrolled in the present study being healthy are not expected to derive any benefit from participating in the present study.

Some changes may be anticipated in humans and thus will be monitored accordingly during the clinical trial as mentioned in section 7.3.1 of the Investigator's Brochure (IB): potential risk of decrease in

appetite, potential risks of alteration of renal and liver function tests, hematology parameters, and glucose levels, as well as potential risk of Central Nervous System alteration. All details on these risks and overall guidance are described in the IB Section 7 (Summary and Guidance for the Investigator).

DNDI-6148 was shown to have no genotoxicity potential. The fertility and reproductive toxicity data available in rats and generated after 64 days of dosing indicate a potential risk for decreasing male fertility. A potential effect on female reproductive performance cannot be excluded in regard to the increase in preimplantation loss and mean number of resorptions observed in the female rats following 21 days of administration. In the absence of animal data on developmental toxicity, risk of human teratogenicity/fetotoxicity cannot be excluded [6]. Of note, no women of childbearing potential are planned to be included in the present clinical trial and measures to prevent any exposure through seminal fluid are in place.

Decrease in fertility in clinical trial participants is not expected, considering the maximum dose considered and duration of treatment planned in the single dose administration study. Findings in male animals, both related to sperm abnormalities and histopathological changes were reported after 64 days of repeated dosing, while no histopathological change was noted in the 28 days repeated dosing study in the same species. The likeliness of impact of a single dose of DNDI-6148 on human male fertility is thus very low.

Before receiving a single dose of DNDI-6148, male participants to the present clinical study should be informed of this concern on the fertility in rat after a long exposure (64 days) while no concern were identified after 28 days, and at a higher exposure than expected in human.

Information on compound from the same chemical class

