3.5.2. Stopping criteria within a cohort

During the treatment period, the safety and tolerability will be evaluated on an ongoing basis, the following criteria will apply to stop the dosing in the cohort:

- 2 subjects experiencing severe non-serious AEs considered as at least possibly related to the study drug
- 2 subjects experiencing a significant increase (i.e. > 5 upper limit of normal value [ULN]) of ALAT.

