3.5.3. Dose escalation Stopping criteria between cohorts

The Safety Review Committee will decide to stop the dose escalation as planned per protocol in case of occurrence of:

- 2 subjects of the same cohort experiencing:
 - a significant increase of ALAT > 3ULN,

- simultaneous increases of total bilirubin > 2ULN, ALAT > 2ULN and alkaline phosphatases > 1.5ULN,
- ➤ 6 subjects of the same cohort experiencing:
 - study drug related moderate, non-serious AEs (that are considered at least possibly related to the drug effect i.e. moderate, non-serious ARs).
- 1 subject of the cohort presenting:
 - a C_{max} or AUC₀₋₂₄ value above 7.3 μg/mL and 65 h*μg/mL, respectively (based on the NOAEL in Cynomolgus toxicology studies).
- The maximum C_{max} and AUC_{0-24} observed in the cohort leads to believe that, taking into account the dose increase, C_{max} or AUC_{0-24} values of 7.3 µg/mL and 65 h*µg/mL might be overpassed with the following planned higher dose.

In one of the cases listed above, the dose group in progress will be stopped and the blind could be broken by the investigator or on request of the sponsor, for one or several volunteers, or the Safety Review Committee could request the support of an independent non-blinded external advisor. Regarding laboratory abnormalities described above, if unblinding confirms that at least two subjects presenting these abnormalities received the active drug, the dose escalation will be stopped.

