8.1.4. Abnormal safety parameters

Before the subject is allowed to enter the study a full clinical evaluation, ECG and full biological test will be obtained and the absence of clinically significant abnormalities confirmed by the Investigator.

In case of abnormality of any safety parameters (clinical, biological and ECG parameters) during the conduct of the study, an assessment on clinical significance of the abnormality will be made and a comment will be recorded in the eCRF; If an abnormality is judged clinically significant, an AE will be recorded.

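### The AE severity scale has no criterion for silent laboratory, vital-sign or ECG events short of risk to life, so non-serious ones cannot count in the severity-based stopping rules

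*Protocol*

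**What the plan says.** **Severity scale (Protocol 8.3.4.1.1).** This is the only scale, and the section says severity will be determined by it.
- Mild: "The subject is aware of the event or symptom, but the event or symptom is easily tolerated".
- Moderate is defined by discomfort great enough to disturb or cut back what the person normally does.
- The Severe grade applies in case of "Significant impairment of functioning: the subject is unable to carry out usual activities", or when the event puts life at risk, or both.
- Life-Threatening and Death follow as separate grades.

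**What counts as an AE.** Section 8.1.4, on clinical, biological and ECG parameters: "If an abnormality is judged clinically significant, an AE will be recorded". Section 8.3.1 treats an abnormality as clinically significant if it suggests disease or organ toxicity and is new or has evolved since screening, or if it needs intervention. Neither condition requires a symptom.

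**Stopping rules that use severity.**
- 3.5.1 stops the trial for severe non-serious related reactions in two subjects of one cohort.
- 3.5.2 stops dosing in the cohort for "2 subjects experiencing severe non-serious AEs considered as at least possibly related to the study drug".
- 3.5.3 stops escalation when six subjects of a cohort have "study drug related moderate, non-serious AEs".

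**Numeric laboratory triggers.** Sections 3.5.2 and 3.5.3 set them for ALAT alone and for bilirubin, ALAT and alkaline phosphatases together. There are no others.

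**Named risks (1.3).** The list includes "potential risks of alteration of renal and liver function tests, hematology parameters, and glucose levels".

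**The concern.** The scale measures how a subject feels and functions. It suits symptoms such as headache or nausea. The laboratory changes the protocol anticipates can be large in someone who notices nothing. The definition of an AE admits these events, but the scale cannot rank them, and the stopping rules then count by rank. The pre-set severity criteria of a first-in-human escalation could stay silent on three of the four laboratory risk areas that the protocol itself names.

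The renal area is not hypothetical. Section 1.2.1.4 reports that the monkey sacrificed at 15 mg/kg had affected electrolytes, urea and creatinine, and that a relationship to the drug could not be fully excluded. The female NOAEL set after that finding is the basis of the starting dose.

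**Working it through.** The protocol states no figure on this point, so there is none to reproduce. The check sets the sections against each other.

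**Step 1. Can a silent laboratory AE be Moderate or Severe?** Take a related, clinically significant abnormality in a subject with no symptoms.
- Mild (8.3.4.1.1) needs awareness. Strictly not met.
- Moderate needs discomfort that interferes with activity. Not met.
- Severe, functional part, needs inability to carry out usual activities. Not met.
- Severe, risk part, needs risk to life. Met only by an extreme event.

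Below risk to life, the event has no defined grade. Mild is the nearest default.

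**Step 2. Does the risk-to-life part bring such events into the severity counts?** The counts in 3.5.1, 3.5.2 and 3.5.3 are restricted to non-serious events. Section 8.3.1 makes an AE serious when the subject was at risk of death at the time. An event that is Severe because life is at risk is therefore serious. If related, it falls under the rule in 3.5.1 that one serious adverse reaction stops the trial. For non-serious events only the functional definitions are left, and step 1 shows that a silent event does not meet them.

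**Step 3. Which named laboratory risks have their own trigger?**

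| Area named in 1.3 | Numeric trigger in 3.5.2 or 3.5.3 |
|---|---|
| Liver | Yes |
| Renal | No |
| Hematology | No |
| Glucose | No |

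That is 1 of 4. QTc is not among the risks named in 1.3. It has no trigger in 3.5 either; the QTc thresholds in section 7 belong to the optional Holter analysis at the end of the trial or later.

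**Step 4. Worked case.** Suppose all 6 active subjects of a cohort have marked, related, silent creatinine AEs, none judged serious. Severe non-serious events: 0, against 2 needed. Moderate non-serious events: 0, against 6 needed. Liver triggers: not involved. No severity or laboratory criterion in 3.5 is met.

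**Step 5. Illustration of size, with an assumed rate.** Let p be the chance that an active subject has a marked, related, silent, non-serious laboratory AE. The documents give no value for p. If every such event were graded Severe by size, the chance that at least 2 of 6 active subjects have one is 1 − (1 − p)^6 − 6p(1 − p)^5.

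| Assumed p | Two-subject rule met, graded Severe by size | As written |
|---|---|---|
| 0.1 | 1 − 0.5314 − 0.3543 = 0.114 | 0 |
| 0.2 | 1 − 0.2621 − 0.3932 = 0.345 | 0 |
| 0.3 | 1 − 0.1176 − 0.3025 = 0.580 | 0 |
| 0.5 | 1 − 0.0156 − 0.0938 = 0.891 | 0 |

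These are upper figures, because a published scale would place some events at Moderate. If all were Moderate and only active subjects had them, the six-subject rule would need 6 of 6, with probability p^6: 0.5^6 = 0.016 even at p = 0.5.

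**The case against.** The case for leaving the text alone has substance.

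- **Other routes to stopping exist.** Under 8.3.1 an important medical event can be serious without symptoms, and one serious related event stops the trial (3.5.1). Section 8.4 halts administration after any SAE. Section 3.3.3.2 puts all out-of-range laboratory values and centrally read ECGs before the Safety Review Committee and allows escalation only if results are acceptable. The sentinel step (3.3.3.1) also uses laboratory data. This stands. A reader might infer that a silent toxicity could not stop the trial; the documents do not support that. These routes rest on judgement, however, and they do not supply a grade.
- **Mild is not assured.** A reader might infer that every silent abnormality is graded Mild whatever its size. The text does not say so: Mild requires awareness, 8.3.1 speaks of clinical intensity with investigator judgement, and risk to life leads to a higher grade. This stands, and the point is limited accordingly.
- **Reporting does not hide the changes.** Laboratory values and changes are described by dose group (11.1.2.3), and 11.1.2.1 lists AE severity but summarises TEAEs by organ class and term. The effect on the final report is therefore small.
- **Confinement.** A reader might infer that the scale fails for symptoms too, because "the subject will be restricted to indoor activities (no exercise), rest and will not leave the Clinical Pharmacology Unit". Ordinary activities such as eating, walking and self-care remain, so that does not follow.
- **Unseen guidance.** Section 1.3 refers to the Investigator's Brochure and 8.3.3 to site procedures. Either might address laboratory grading. Section 8.3.4.1.1 nevertheless prescribes its own scale and points to no other.
- **Functional grading is a legitimate choice.** True for symptoms. The difficulty arises because the protocol admits symptom-free AEs and then uses grade to trigger stopping.

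**Conclusion.** The point holds in limited form. Read as written, 8.3.4.1.1 cannot place a silent, non-serious laboratory, vital-sign or ECG AE at Moderate or Severe, so such AEs do not contribute to the severity counts in 3.5.1 to 3.5.3. Three of the four laboratory risk areas in 1.3 have no numeric trigger to compensate. The conclusion rests on two readings: that the functional definitions are applied literally, and that an event with actual risk to life is always classed as serious under 8.3.1.

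The probabilities illustrate what the gap could mean under assumed rates; they are not estimates for this drug. The seriousness route and the mandatory Committee review limit the consequence. It should be corrected because severity is a stopping trigger and the correction is cheap, but it does not leave subjects without safeguards.

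**What to change.** In 8.3.4.1.1, state that AEs defined by a laboratory, vital-sign or ECG value are graded on the size of the abnormality, using one published scale that the sponsor names and maps to Mild, Moderate and Severe. Keep the present functional definitions for symptoms.

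The sponsor should then reconcile 8.3.4.1.1 with the laboratory AE definition in 8.3.1, the stopping rules in 3.5.1 to 3.5.3 and the risks in 1.3, since graded laboratory events would begin to enter those counts. No threshold or stopping count is proposed here.

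**Cost.** One amendment paragraph and eCRF completion guidance. Some laboratory AEs will be graded higher than under the present text. Completed cohorts, which include at least the 10, 20 and 40 mg groups whose interim results 3.3.3.2 cites, need regrading from values already collected.

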8.3.4.1.2. Adverse Event causality assessment

The Investigator will evaluate the possible relationship between the AE and the study drug, i.e. to determine whether there exists a reasonable possibility that the trial drug(s) caused or contributed to the AE(s) and will transmit the result of this evaluation to the Sponsor.

The possible relationship between the AE and the study drug will be quoted as following:

Not related: There is no reasonable possibility of causal relationship.

Related: There is at least a reasonable possibility of a causal

relationship between an adverse event and an investigational medicinal product. This means that there are facts (evidence) or arguments to suggest a causal

relationship.

To help investigators with the decision binary tree yes/no (i.e. Related/Not related) in the evaluation of causality, the Council for International Organizations of Medical Sciences (CIOMS VI) group recommends that investigators be asked to consider the following before reaching a decision:

- Medical history (including presence of risk factors)
- Lack of efficacy/worsening of existing condition
- Study medications
- Other medications (concomitant or previous)
- Withdrawal of study medication, especially following trial discontinuation / end of study medication
- Erroneous treatment with study medication (or concomitant)
- Protocol related procedure

